## 5. Inclusion/Exclusion Criteria

Our study population will be treating radiation oncologists and their primary cancer patients requiring definitive treatment with radiation with or without concurrent chemotherapy as per the inclusion criteria below. Cancer patients receiving stereotactic body radiation therapy or hypo-fractionated definitive radiation will not be recruited as these patients represent a different treatment population with a much lower overall treatment toxicity burden.

### **Patients:**

#### Inclusion Criteria:

- Men and women over 18 years of age
- Able to read and write in English or able to understand/answer questions with the aid of an interpreter
- Histologically confirmed loco-regional to advanced primary cancer, including but not limited to lung cancer, esophageal, or gastro-intestinal cancers at risk of developing radiotherapy-related toxicity.

- Receiving definitive conventionally-fractionated radiation treatment with or without chemotherapy

**Exclusion Criteria:**

- Patients receiving radiation for palliative intent
- Patients who do not provide informed consent
- Patients who chose to withdraw from the study

**Radiation Oncologists**

**Inclusion criteria:**

- Must be the physician overseeing the care of the patient who answers the PROMS

**Exclusion criteria:**

- Have not provided informed consent

**6. Drugs/ Substances/ Devices**

- a. The rationale for choosing the drug and dose or for choosing the device to be used.  
Not applicable.
- b. Justification and safety information if FDA approved drugs will be administered for non-FDA approved indications or if doses or routes of administration or participant populations are changed.  
Not applicable.
- c. Justification and safety information if non-FDA approved drugs without an IND will be administered.  
Not applicable.

**7. Study Statistics**

This is a prospective pilot study.

- a. Primary outcome variable(s).

*The primary outcome is the proportion of patients with any change in their physician-assessed burden scores for at least one on-treatment visit, along with their exact binomial 95% confidence interval.*

- b. Secondary outcome variables

*The secondary outcome is the proportion of patients with a change in their on-treatment management for at least one on-treatment visit, along with the exact binomial 95% confidence interval.*

- c. Exploratory outcome variables:

We will also summarize the mean change in the physician-assessed burden score across on-treatment-visits, and across patients, using mean, standard deviation, median and ranges. We will report the distribution of changes (an increase, decrease or no change) in physician burden score after PROM review across all visits.

We will also summarize the mean change in the physician interventions across on-treatment-visits, and across patients, using mean, standard deviation, median and range of cumulative changes in interventions made. We will explore the average cumulative number of management interventions based on each specified numerical change in burden score.

*Additionally, we will describe differences in mean physician burden score between first half and second half of treatment.* To describe changes in the physician perception of treatment-related toxicity resulting from routine physician review of PROMs, we also will compare the mean change in burden scores for on-treatment visits 4 to 7 to the mean change in burden scores for visits 1 to 3. Treatment-related toxicities are expected to worsen over time. If PROM review does not change physician perception of treatment-related symptoms, there would no difference between the mean change in burden score across patients in the first half of treatment compared to the second half of treatments. Using paired t-tests, we will examine the differences between mean physician burden score across patients in the second compared to the first half of the treatments. We would expect the changes in burden scores to be greater in later visits since treatment-related toxicities and corresponding PROMS are expected to worsen over time.

*Depending on the proportion of patients with a change in physician burden assessment, we will also explore potential variables associated with a change in burden assessment by the physician.*

We will evaluate associations between variables of interest and development of any point as well  $\geq 2$  absolute point change in their physician's assessed burden scores for at least one on-treatment visit using Fisher's exact test. Variables may include but are not limited to: PROM question type from the corresponding on-treatment visit (symptom type, symptom severity, most bothersome symptom, interference on activity of daily living), baseline clinical or demographic information, and/or treatment information including treating-physician or disease-site. We will not adjust for multiple comparison due to the exploratory nature of this study.

d. Statistical plan including sample size justification and interim data analysis.

The analyses will be descriptive. The statistical plan is written by study objective above. Exploratory plots will be made (line graph, bar plots) and used to visualize the distribution of data of interest. These plots may include but are not limited to cumulative number of additional interventions recommended with time and the distribution of type of additional interventions (counseling, medications/interventions, referrals, testing/evaluation). Exploratory tables will compare the average burden score change with the average cumulative number of management interventions per week. Secondary analysis will explore ratings on the Clinician Feedback Form.

Annually, 60-80 lung and esophageal cancer patients and 20 gastrointestinal tumors are treated with definitive RT over the course of 5-7 weeks at Johns Hopkins. On average  $>80\%$  of on-treatment visits have PROMs completed for lung cancer patients. A sample size of at least 50 patients yields a two-sided 95% confidence interval with a width of less than 30% for descriptive analyses. Thus, we would be able to estimate the proportion of patients with a change in their physician assessed burden score and change in management with a margin of error of 15 % ( $\pm 15\%$ ).

There will be no interim data analysis.

e. Early stopping rules.

Not applicable.

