As a part of the study, treating physicians over-seeing the care of their patients will be asked to provide a global burden score. Lee et al. demonstrated the feasibility of using a global burden score to capture the provider's overall perception of the combined burden of *all* assessed symptoms, using a visual analogue scale demarcating an aggregate score from 0 to 10. This scale uses anchors at 0, 2, 4, 6, 8, and 10 for no, mild, moderate, severe, life-threatening adverse events, and death, respectively.

\*\* During weekly on-treatment visits and prior to reviewing their patient's PROMs, physicians will rate the symptom burden for each of their patients from 0 to 10 using available clinical data. Routine available clinical data include: vital signs, laboratory work, physical exam, nursing assessment, physician's clinical judgement. Then after reviewing the patient's PROMs, physicians will re-rate the patient's symptom burden and report any change in recommended interventions due to review of the PROMs. Management changes include (1) additional counseling, (2) medications/interventions changed, (3) referrals to other services, and (4) further testing/evaluation (**Appendix B**). At the end of each patient's course of radiotherapy, providers will complete a Clinician Feedback Form to answer questions regarding the impact of PROM review on overall symptom perception and management during treatment (**Appendix C**). These forms were designed to be easy to complete and will take an estimated 5 minutes per patient.

\*\*At the time of enrollment, research staff will collect pertinent patient baseline and characteristics through clinical chart review. During each on-treatment visit, research staff collect pertinent clinical and treatment variables through chart review (**Appendix D**). The research staff, if available on site, will also be available to assist patients in completing the questionnaires during scheduled visits and to address any issues or concerns patients have in completing the questionnaires.

\*\* Marks demarcates interventions that will/may require research staff availability and assistance.

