- b. If your study involves data/biospecimens from participants enrolled under other research studies with a written consent or under a waiver of consent, please list the IRB application numbers for those studies. Please note: Certificate of Confidentiality (CoC) protections applied to the data in source studies funded by NIH or CDC will extend to this new study if the funding was active in 2016. If this situation applies, Section 36, question 4 in the application will need to be answered "Yes" and "Hopkins Faculty" should be selected in question 7. No other documents are required.

Not applicable.

- c. Study duration and number of study visits required of research participants.

Patients will be enrolled in the study prior to or on their first radiotherapy on-treatment visit and will continue through the course of their radiotherapy. Data will be collected at routine weekly on-treatment visits; no study-specific visits are required

d. Blinding, including justification for blinding or not blinding the trial, if applicable.

Blinding will not be possible as the treating physician will need to provide routine care to the patients enrolled on this study. In addition, the treating physician will need to appropriately assign burden scores, and to report on whether there was a change in management for each of their patients who enroll on this study.

e. Justification of why participants will not receive routine care or will have current therapy stopped.

Patients will continue to receive their routine care. This study will not alter nor stop the planned radiotherapy treatments. All patients enrolled will undergo routine weekly on-treatment evaluation and toxicity management by the treating physician.

f. Justification for inclusion of a placebo or non-treatment group.

There is NO placebo group. This is a pilot study to evaluate whether physician review of PROMs during radiotherapy changes the physician's assessment of a cancer patient's overall toxicity burden and management of treatment-related symptoms. There is insufficient sample size to include a placebo group. In future studies building on this, where we have a greater sample size, we can randomize patients to 2 arms: with and without routine PROM review.

g. Definition of treatment failure or participant removal criteria.

Patients will be removed if they desire to refrain from answering the PROM questionnaire.

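### The ever-change outcome depends on how many PROM-reviewed visits a patient has, so Fisher's tests by disease site or physician can reflect course length or completion alone

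*Combined protocol and SAP*

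**What the plan says.** All references are to the combined protocol and SAP.

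- **Primary outcome (Section 7a):** "the proportion of patients with any change in their physician-assessed burden scores for at least one on-treatment visit", reported "along with their exact binomial 95% confidence interval". The secondary outcome (Section 7b) has the same at-least-one-visit form for management changes.
- **How a change arises (Section 4, Study Procedures):** the physician scores burden before seeing the PROM. Afterwards, "physicians will re-rate the patient's symptom burden and report any change in recommended interventions due to review of the PROMs".
- **Number of visits:** "Data will be collected at routine weekly on-treatment visits" (Section 4c), and patients are "treated with definitive RT over the course of 5-7 weeks at Johns Hopkins" (Section 7d). That is about 5 to 7 scheduled visits.
- **Completion (Section 7d):** on average more than 80% "of on-treatment visits have PROMs completed for lung cancer patients". No figure is given for esophageal or gastrointestinal patients, or for the second institution.
- **Missed PROMs:** Section 4g removes patients who do not wish to answer the questionnaire, and Section 8 lets patients stop at any time. No rule covers a single visit without a PROM, and nothing says whether removed patients stay in the denominator.
- **Exploratory work (Section 7c):** the distribution of increases, decreases and no changes after PROM review will be reported over all visits. Fisher's exact test will relate ever-change (any change, and a change of 2 points or more) to variables that may include disease site, treating physician and PROM items from the corresponding visit.
- **Precision (Section 7d):** "A sample size of at least 50 patients yields a two-sided 95% confidence interval with a width of less than 30% for descriptive analyses".

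**The concern.** A visit without a PROM cannot yield a change, yet the patient can still count as unchanged. The patient-level result therefore combines two things: how often a review changes the physician's score, and how many reviews took place. The primary objective concerns the first, in the setting of routine review.

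The group comparisons carry the larger risk. Disease sites can differ in course length, and sites or physicians can differ in completion. Fisher's test on ever-change takes no account of either, so a difference in the number of reviews can look like a difference in how physicians respond to PROMs. There is also a mismatch of level: PROM answers belong to a visit, whereas ever-change belongs to a patient, and a patient who never changed has no particular visit to which the PROM answer would correspond.

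**Working it through.** **1. The plan's own figure.** At n = 50 the widest exact (Clopper-Pearson) 95% interval occurs at 25/50: 35.5% to 64.5%, width 28.9 points, half-width 14.5. The statement of a width below 30% is correct. It covers sampling error only.

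**2. Inputs.** Scheduled visits K = 5 to 7 (weekly visits, 5 to 7 weeks). Completion c = 0.80, the lower bound of the plan's figure. The probability q that a reviewed visit produces a change is not in the documents; I assume 0.05 to 0.30, constant over visits and, at first, independent between visits.

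**3. Formula.** P(ever change) = 1 − (1 − q·c)^K.

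**4. Full versus 80% completion.**

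| q | K | c = 100% | c = 80% | Difference (points) |
|---|---|---|---|---|
| 0.05 | 5 | 22.6% | 18.5% | about 4 |
| 0.10 | 6 | 46.9% | 39.4% | 7.5 |
| 0.15 | 6 | 62.3% | 53.6% | 8.7 |
| 0.20 | 5 | 67.2% | 58.2% | about 9 |
| 0.20 | 6 | 73.8% | 64.9% | 8.9 |
| 0.30 | 7 | 91.8% | 85.4% | 6.4 |

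For example, at q = 0.15 and K = 6: 1 − 0.85^6 = 62.3%, and 1 − (1 − 0.12)^6 = 1 − 0.88^6 = 53.6%. Over the whole range of q and K the shift is about 4 to 9 points.

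**5. Relaxing independence.**

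- *Changes correlated within patient* (beta-distributed patient rates, mean 0.15, K = 6, c = 0.80; the correlations are assumptions): the shift is 8.7 points at correlation 0, 6.6 at 0.1, 4.0 at 0.3 and 2.4 at 0.5.
- *Missing PROMs clustered in patients* (80% of patients complete all, 20% none; q = 0.20, K = 6): 0.8 × 73.8% = 59.0%, a shift of about 15 points from 73.8%. This is an extreme case and applies only if those patients stay in the denominator.

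**6. Group comparison.** With equal completion (80%) and equal q = 0.15, only course length differs:

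- 5 visits: 1 − 0.88^5 = 47.2%
- 7 visits: 1 − 0.88^7 = 59.1%

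The gap is about 12 points with no difference in the effect of review. At q = 0.10 and full completion the corresponding figures are 41.0% and 52.2%.

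**7. Would restricting the denominator help?** At 80% independent completion, the share of patients with no reviewed visit is 0.2^6 = 0.006% at K = 6 and 0.2^5 = 0.03% at K = 5. Requiring at least one reviewed visit leaves the 53.6% in step 4 at 53.6%.

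**The case against.** The strongest reply is that the objective concerns routine physician review. In routine practice some PROMs are not completed, so the ever-change proportion describes what actually happens. A reader might infer from step 4 that the primary result understates the truth. The documents do not support that: the figure is low only against full completion, which the plan never sets as its target. This part of the objection stands, although the plan does not state that it intends the routine-practice reading.

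A reader might also compare a patient with 2 reviewed visits and one with 7 (28% versus 68% at q = 0.15) and expect 40-point distortions between groups. That is a contrast between individuals. At 80% completion only 1.7% of 6-visit patients have 2 or fewer reviewed visits, and the documents give no completion figures by site or physician. The 12-point contrast is the one that the 5 to 7 weeks support at equal completion and that rate.

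Three further points hold in part:

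- The planned distribution of changes over all visits already gives most of a per-visit view. It lacks an explicit denominator and an interval.
- The 80% comes from existing clinic collection. The study adds staff checks, a paper back-up and research-staff help where available, so completion may be higher.
- The Fisher's tests are optional and labelled exploratory. That excuses the absence of multiplicity adjustment, but it does not remove confounding with the number of reviews.

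**Conclusion.** The concern holds in a limited form. The primary proportion is valid as a description of routine practice, but it depends on the number of PROM-reviewed visits and should not be read alone as the effect of review. Moving from full to 80% completion lowers it by about 4 to 9 points if changes are independent with per-visit rates of 5% to 30%. That is inside the planned 15-point margin, but the margin does not cover it. Within-patient correlation makes the shift smaller and clustered missingness makes it larger, so its true size is unknown. The clearest weakness is in the exploratory associations, where course length alone can give 47% versus 59% (assumed 15% rate, 80% completion). Neither the primary outcome nor the sample size needs to change.

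**What to change.** 1. Keep the primary outcome and n = 50. Report it with the distribution of PROM-reviewed visits per patient, and state how visits without a PROM and removed patients are counted.
2. Extend the planned visit-level distribution to the proportion of PROM-reviewed visits with a change, with a 95% confidence interval clustered on patient. Do the same for management changes.
3. For the exploratory associations, use a logistic GEE on reviewed visits, clustered on patient, or otherwise account for the number of reviewed visits. This can replace Fisher's test on ever-change or stand beside it. It also places visit-level PROM answers at the level where they were measured.

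The cost is SAP wording and one additional analysis of data already being collected. The drawbacks are a second estimate to explain and physician-level results that may be unstable with about 50 patients, so those should stay exploratory.

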Patient-reported outcome measures (PROMs) is an umbrella term that refers to any report on a health status measure that is reported directly by the patient, without the influence of clinicians or anyone else. PROMs have been shown to more closely reflect a patient's daily health status when compared to physician-reported measures. Given the disconnect between patient and provider-assessed toxicity, PROMs can be used to more accurately and consistently characterize the detrimental impact of treatment on a patient's symptom-specific outcomes, functional well-being, and overall quality of life. For example, a French randomized trial in stage IV NSCLC patients showed a survival benefit (22.5 vs 14.9 months) when using web-based PROMs to guide follow-up vs. standard follow-up with imaging every 3 to 6 months. However, research is needed to evaluate if patient symptom reporting during treatment allows earlier and improved detection of treatment toxicity, and leads to individualized interventions which may improve the toxicity outcomes for locally-advanced and oligometastatic patients receiving definitive chemoRT.

**2. Objectives** (include all primary and secondary objectives)

- a. Primary objective:** Describe the proportion of patients with changes in physician-perception of treatment-related toxicity that result from routine physician review of PROMs reported during definitive radiotherapy.
- b. Secondary Objectives:** Describe (1) the proportion of patients with changes in the management of treatment-related symptoms and (2) the type of management changes that result from routine physician review of PROMs reported during definitive radiotherapy.

**3. Background** (briefly describe pre-clinical and clinical data, current experience with procedures, drug or device, and any other relevant information to justify the research)

[figure not shown]

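### The early-versus-late comparison in 7c appears to use a signed mean change, so re-ratings that grow in both directions could show as no difference

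*Combined protocol and SAP*

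**What the plan says.** The primary objective (section 2) is direction-free: "Describe the proportion of patients with changes in physician-perception of treatment-related toxicity". The outcome in 7a follows it: "The primary outcome is the proportion of patients with any change in their physician-assessed burden scores for at least one on-treatment visit". A rise and a fall both count.

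Section 7c then describes the size of change. Overall: "We will also summarize the mean change in the physician-assessed burden score across on-treatment-visits, and across patients, using mean, standard deviation, median and ranges". By direction: "We will report the distribution of changes (an increase, decrease or no change) in physician burden score after PROM review across all visits". By time: "we also will compare the mean change in burden scores for on-treatment visits 4 to 7 to the mean change", where the reference group is the first three visits. The plan adds that if PROM review leaves perception unaltered, the mean change should not differ between the two halves, and that larger changes are expected later because toxicity worsens.

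The test is worded differently; its sentence begins "Using paired t-tests, we will examine the differences between mean physician burden score across patients in the second compared to the first half of the". That sentence names the burden score, not the change in it.

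Section 7d adds a weekly table: "Exploratory tables will compare the average burden score change with the average cumulative number of management interventions per week". The word absolute is used only for the 2-point threshold in the Fisher's exact analyses. The hypothesis at the end of section 3 is directional: it expects physicians' burden assessments to rise.

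**The concern.** A mean change with no qualifier is normally read as after minus before, with its sign. The authors wrote absolute for the Fisher threshold and not here, which supports that reading. On it, one visit re-rated up a point and another re-rated down a point average to zero, although the physician's view moved at both.

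This matters most for visits 4-7 versus 1-3, because that comparison comes with a rule for interpreting it. The plan states the rule in one direction: no PROM effect implies no difference. A reader who finds no difference will be inclined to run it backwards and conclude that PROM review had no influence. With a signed mean, that conclusion could be drawn even when re-ratings had become markedly more common. The increase/decrease/no-change distribution would reveal two-way movement, but it is planned over all visits together and so does not show what happened in each half.

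**Working it through.** **The plan's own figure.** The documents give no SD, effect size, significance level or power for the halves comparison. The only related figure is the 95% interval width below 30% at 50 patients (7d). The exact binomial interval is widest at 25/50: 35.5% to 64.5%, a width of 28.9%. The figure reproduces, and this point does not touch it.

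**Inputs.** From the plan: 50 patients; early visits 1-3; late visits 4-7. Assumed, because the documents give none: each re-rating is +1, -1 or 0; visits are independent; two-sided 0.05; and the up/down rates below.

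**Formulas.** Let u and d be the shares of visits re-rated up and down.
- Signed: mean per visit = u - d; variance = (u + d) - (u - d)².
- Absolute: mean per visit = u + d; variance = (u + d)(1 - u - d).
- Standard error of the late-minus-early difference = √[(early variance/3 + late variance/4)/50].

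**Both directions double, 10%/10% to 20%/20%.**
- Signed: difference = (0.20 - 0.20) - (0.10 - 0.10) = 0.00. With no expected difference the test rejects at its nominal 5%.
- Absolute: difference = 0.40 - 0.20 = 0.20; standard error = √[(0.16/3 + 0.24/4)/50] = 0.048; ratio = 0.20/0.048 ≈ 4.2.

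**Mostly upward, 15%/5% to 30%/10%.**
- Signed: difference = 0.20 - 0.10 = 0.10; standard error = √[(0.19/3 + 0.36/4)/50] = 0.055; ratio ≈ 1.8.
- Absolute: difference = 0.20, as above.

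**Simulated rejection rates** (4,000 trials per row, paired t-test, 3 early and 4 late visits):

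| Up/down, early to late | Expected difference, signed | Expected difference, absolute | Rejects, signed | Rejects, absolute |
|---|---|---|---|---|
| 10/10 to 20/20 | 0.00 | 0.20 | 5% | 98% |
| 15/5 to 25/15 | 0.00 | 0.20 | 5% | 98% |
| 12/8 to 24/16 | 0.04 | 0.20 | 11% | 98% |
| 15/5 to 30/10 | 0.10 | 0.20 | 44% | 98% |
| 20/0 to 40/0 | 0.20 | 0.20 | 98% | 98% |

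With no change in rates (10/10 in both halves) both versions reject at about 5%, as they should.

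**Shorter courses.** Treatment lasts 5-7 weeks (7d) with weekly visits, so some patients have only 5 - 3 = 2 late visits. With 2-4 late visits, 10/10 to 20/20 gives 5% versus 96%. With five of every six re-ratings upward (10/2 to 20/4) it is 38% versus 74%. All upward (10% to 20%) it is 66% for both.

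**The tested variable.** If the t-test is run on the burden score itself, as its sentence says, it addresses another question. The plan expects toxicity to worsen, so the score would be expected to rise between halves whether or not PROM review altered any rating.

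**The case against.** The strongest reply is that a signed mean suits this study. Section 3 hypothesises upward re-rating, the abstract says physicians under-report symptoms, and the halves comparison rests on worsening toxicity. Listing decreases as a reporting category does not mean that the authors expect many. This stands: the signed mean should be kept, and if all re-ratings are upward nothing is lost.

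The rates above are also assumptions, and the two columns test different quantities, so they are not two powers for one hypothesis. Absolute change includes re-rating noise. On a 0-10 scale, low early scores leave little room to fall, so absolute change could grow later for that reason alone. These points stand too, and they argue for showing both measures.

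A reader might infer three stronger things that the documents do not support.

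- **That every summary of size hides two-way movement.** The overall summary includes the SD, the range and the direction counts. With 1-point re-ratings at 20%/20%, the visit-level SD is √0.40 = 0.63 even though the mean is zero. The weekly table does average changes, but 7c also plans to relate interventions to each numerical change in score, which keeps +1 and -1 apart. Those two places are largely covered.
- **That a near-zero halves difference would contradict a high primary proportion.** It would not. The primary outcome is any change over the whole course; the halves statistic is a difference over time. Upward re-ratings at a constant rate would give a high proportion and no halves difference, signed or absolute.
- **That the plan specifies a paired t-test on signed change.** Signed is inferred, and the t-test sentence names the burden score.

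**Conclusion.** The point holds for the comparison of visits 4-7 with visits 1-3, and its severity is minor. On the ordinary reading this is a signed mean used to describe changes in perception, with no measure of size and no direction split by half beside it. The loss runs from none, if all re-ratings are upward, to complete, if both directions grow by equal amounts. In between, under the assumed rates, the signed comparison rejects in 11% to 44% of trials where the absolute one rejects in 98%. Where the study will fall in that range cannot be known from the documents. The analysis is exploratory in a descriptive pilot and carries no decision. If the authors meant absolute change, the cancellation disappears but the text still needs to say so.

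**What to change.** In 7c:

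1. Define change as the burden score after PROM review minus the score before it.
2. Name that change as the variable in the paired t-test. If the raw burden score is also to be compared between halves, list it separately.
3. For visits 1-3 versus 4-7, report the mean absolute change, for size, beside the signed mean, for direction.
4. Give the increase/decrease/no-change distribution separately for each half.

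The cost is a few sentences and one extra exploratory comparison from scores already collected. Because absolute change includes re-rating noise, it should stand beside the signed mean and not replace it.

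### The paired t-test comparing the two halves of treatment names the burden score, while the comparison, null and expected result around it concern the change in score after PROM review; the test variable must be stated

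*Combined protocol and SAP*

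**What the plan says.** All of this stands in one paragraph of section 7c (exploratory outcome variables), apart from the rating procedure.

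- The paragraph opens on the score: "we will describe differences in mean physician burden score between first half and second half of treatment".
- It then turns to the effect of PROM review and to the change in score, with the first three visits as the comparator: "we also will compare the mean change in burden scores for on-treatment visits 4 to 7 to the mean change in burden scores".
- It gives the expected time course: "Treatment-related toxicities are expected to worsen over time".
- The null, which sets the first half against the second, is on the change: "If PROM review does not change physician perception of treatment-related symptoms, there would no difference between the mean change in burden score".
- The test is on the score: "Using paired t-tests, we will examine the differences between mean physician burden score across patients in the second compared to the first half".
- The expected result is again on the change: "We would expect the changes in burden scores to be greater in later visits".

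Section 4a (Study Procedures) provides two ratings at each weekly visit, both on a 0 to 10 scale: one before the physician sees the PROMs and one after. The change is the second minus the first.

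Elsewhere in section 7c the change in score is summarised by mean, standard deviation, median and range ("We will also summarize the mean change in the physician-assessed burden score across on-treatment-visits"), and by direction ("We will report the distribution of changes (an increase, decrease or no change) in physician burden score after PROM review across all visits").

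**The concern.** The score and the change in score answer different questions. The score in the second half minus the score in the first half measures how toxicity develops during radiotherapy. The same contrast on the change measures whether the shift produced at PROM review is larger late in treatment than early.

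The null and the expectation on either side of the test sentence are about PROM review. If the test is run on the score as written, a significant result would be read against that null and could be reported as an effect of PROM review, when the rise in toxicity that the plan already expects is enough to produce it. Two analysts could also run different tests from this text: on the score before review, the score after review, or their difference.

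**Working it through.** **The plan's own figure.** None is given for this comparison. The only precision figure, in section 7d, concerns the proportions: at least 50 patients give a 95% interval narrower than 30%. It reproduces. The widest exact interval at n = 50 is 35.5% to 64.5% (25 of 50), a width of 28.9 points. It is not in question here.

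**Inputs from the documents.** n = 50; 5 to 7 weeks of treatment with weekly visits; first half = visits 1 to 3, second half = visit 4 onward.

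**Inputs assumed.** 5, 6 or 7 visits equally likely; a linear rise in the score of b points per visit; independent visit-level deviations with SD s; no effect of PROM review; no missed visits; no allowance for the bounded scale.

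**Step 1: expected difference in the score between halves.** The mean visit number is 2 in the first half. In the second half it is 4.5, 5.0 or 5.5 for 5, 6 or 7 visits. The expected difference is therefore 2.5b, 3.0b or 3.5b, on average 3.0b. At b = 0.1 this is 0.30 point, with PROM review doing nothing.

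**Step 2: its standard error.** The variance of one patient's difference is s² × (1/3 + 1/m), where m is the number of second-half visits (2, 3 or 4). The bracket is 0.833, 0.667 or 0.583, on average 0.694. Unequal visit numbers add b² × 0.167, which is 0.0017 at b = 0.1. At s = 1.0 the SD is √0.696 = 0.834 and the standard error is 0.834/√50 = 0.118.

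**Step 3: rejection rate.** The noncentrality is 0.30/0.118 = 2.54. A two-sided 5% t-test on 49 degrees of freedom then rejects in about 70% of trials. Simulation with 20,000 runs per cell agrees:

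| Rise per visit | s = 0.75 | s = 1.0 | s = 1.5 |
|---|---|---|---|
| 0 | 5% | 5% | 5% |
| 0.05 | 39% | 24% | 13% |
| 0.1 | 91% | 70% | 38% |
| 0.2 | 100% | 99.8% | 91% |

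If slopes also differ between patients (SD 0.2), the row for 0.1 falls to 66%, 52% and 32%.

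**Step 4: the same test on the change.** The trend is in both ratings of a visit, so it drops out of after minus before. With no PROM effect, simulation gives about 5% rejection at every slope tried (0 to 0.5 point per visit). With a constant shift c at every visit the contrast is c − c = 0, and the test again rejects in about 5% (4.7% to 5.2% for shifts of 0.25 to 1.0 point). If the shift grows by 0.1 point per visit, the test rejects in 38% to 99.9%, depending on the assumed SDs. On the change, then, this is a test of whether the shift varies over treatment.

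**The case against.** The strongest reply is that context settles the matter: the comparison, the null and the expectation are all on the change, so the test sentence has simply lost a word and no careful analyst would be misled. That is plausible but cannot be established. The paragraph's opening sentence also names the score, in almost the same terms as the test sentence, and the next sentence is worded as an additional comparison. The authors may intend two analyses: a raw-score comparison, with the t-test, describing the course of toxicity, and a separate comparison of changes. On that reading the raw-score test is no mistake, but the comparison meant to describe PROM review has no named test. The variable needs stating on either reading.

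It is also fair to say that the rejection rates do not quantify this trial, since every slope and SD is assumed. The direction needs no simulation.

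Three stronger readings might be inferred and are not supported:

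- That the plan would take equal halves as proof of no PROM effect. It says only that no effect implies equal halves and does not assert the converse. A constant shift would also give equal halves, which is a reason to label the comparison clearly, but the plan draws no wrong inference here.
- That the mean-change summary is defective without a confidence interval. Section 7d calls the analyses descriptive, and an interval would be an optional addition.
- That a difference on the change would by itself establish an effect of PROM review. There is no control group, so a shift from the act of re-rating cannot be separated from it.

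**Conclusion.** The concern holds as an unstated test variable with a real consequence under one literal reading. Run on the score and read against the stated null, the test would tend to favour a difference that reflects worsening toxicity. This follows from the plan's own expectation and does not depend on the assumed figures. The size does: 13% to 91% rejection for rises of 0.05 to 0.1 point per visit with a shared slope and visit-level SDs of 0.75 to 1.5, and about 5% if there is no rise.

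Whether a word was dropped or two analyses were meant cannot be decided from the documents.

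Severity is minor. One exploratory comparison is affected. The primary proportion with any change in burden score, the secondary proportion with a change in management, their exact intervals and the distribution of increases, decreases and no change all stand.

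**What to change.** 1. State that the paired t-test bearing on PROM review uses each patient's mean same-visit change (score after review minus score before review), visits 4 to 7 against visits 1 to 3.
2. Describe that comparison as variation of the shift over the course of treatment.
3. If raw scores are also compared by half, say which rating is used and label the result as the course of toxicity and not as evidence about PROM review.

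These are wording changes and cost nothing in patients, visits or forms. They should be made before analysis.

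Optionally, add a 95% confidence interval for the mean within-visit change, using one mean per patient, to the planned summary. Under assumed between-patient SDs of 0.5 to 1.0 and within-patient SDs of 0.5 to 1.5, its half-width at n = 50 would be about 0.15 to 0.33 point. Three limits should be reported with it:

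- One mean per patient deals with repeated visits but not with clustering by physician. With 4 to 10 physicians and an intraclass correlation of 0.02 to 0.10 (both assumed), true coverage would be about 94% down to 82%.
- Without a control, excluding zero cannot separate PROM review from re-rating.
- Increases and decreases can cancel in the mean, so it should be read beside the planned distribution of directions.
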